7.3 LOST TO FOLLOW-UP

A participant will be considered lost to follow-up if he or she fails to return for two consecutive scheduled visits and is unable to be contacted by the study site staff.

The following actions must be taken if a participant fails to return to the clinic for a required study visit:

- The site will attempt to contact the participant within 24 hours and reschedule the missed visit within two weeks and counsel the participant on the importance of maintaining the assigned visit schedule and ascertain if the participant wishes to and/or should continue in the study.

- Before a participant is deemed lost to follow-up, the investigator or designee will make every effort to regain contact with the participant (where possible, 3 telephone calls and, if necessary, a certified letter to the participant's last known mailing address or local equivalent methods). These contact attempts should be documented in the participant's medical record or study file.
- Should the participant continue to be unreachable, he or she will be considered to have withdrawn from the study with a primary reason of lost to follow-up.

8 STUDY ASSESSMENTS AND PROCEDURES

8.1 EFFICACY ASSESSMENTS

8.1.1 PRE-STUDY PROCEDURES

To be performed no more 4 weeks prior to initiation of study treatment

Imaging: CT chest, abdomen, and pelvis with IV contrast

To be performed within 1 week of 1st study treatment evaluation

Informed consent, demographics, concomitant medications, performance status, physical examination, vitals, height, weight, complete blood count, complete metabolic panel, serum pregnancy test completed within 72 hours of enrollment, serum HSV1 Ab, electrocardiogram, tumor measurement by palpation/exam, request slides from tumor biopsies for immunohistochemical analysis.

Week 1 procedures:

Complete blood count, complete metabolic panel, pharmacy to begin thawing/preparation of dose, clinic visit with concurrent medications, performance status, physical examination, vitals, weight, tumor measurement by examination, injection of T-VEC into primary tumor.

Weeks 2, 3 and 6:

Clinic visit with concurrent medications, performance status, physical examination, vitals, weight, anti-HSV Ab titer on week 6 only

Bi-weekly procedures starting Week 4-week 52:

Complete blood count, complete metabolic panel, pharmacy to begin thawing/preparation of dose, clinic visit with concurrent medications, performance status, physical examination, vitals, weight, tumor measurement by examination, injection of T-VEC into primary tumor.

Off-study procedures:

Complete blood count, complete metabolic panel, clinic visit with concurrent medications, performance status, physical examination, vitals, weight, and punch biopsy all within 30 days of last study treatment. Follow up of any treatment-related adverse events until resolution, stabilization, or death for a minimum of 30 days after last study treatment. Data on any perioperative complications should be also collected as applicable. Final tumor

measurement/assessment will be done based on the postoperative pathology report when available in the electronic medical record to assess degree of pathologic response to neoadjuvant therapy. Long-term follow up for disease recurrence/vital status/occurrence of any suspected herpetic infectious events up to 2 years after the off study visit date by telephone contact and/or clinical assessment at least once every 6 months (+/- 1 month) should be done. Patients and their close contacts should be instructed to notify the study team immediately regarding any suspected new herpetic infection events so that clinical evaluation of the event by the patient's health care provider, PCR testing of any lesions, expedited reporting (within 24 hours of notification) to Amgen at [name] and to the FDA, and treatment as clinically indicated can be completed.

8.1.2 EFFICACY ANALYSES

For the purposes of meeting the secondary endpoints of this study, patients will be re-evaluated for response every 2 weeks prior to injection using physical examination and measurement with calipers and/or ruler.

In addition to baseline imaging, imaging should also be obtained 12 weeks following initial documentation of objective response.

8.1.2.1 DEFINITIONS

Evaluable for toxicity. All patients will be evaluable for toxicity from the time of their first treatment with T-VEC

Evaluable for objective response. Only those patients who have measurable disease present at baseline, have received at least three injections at the 10^8 dose level, and have had their disease re-evaluated will be considered evaluable for response. These patients will have their response classified according to the definitions stated below.

Evaluable Non-Target Disease Response. Patients who have lesions present at baseline that are evaluable but do not meet the definitions of measurable disease, have received at least one cycle of therapy, and have had their disease re-evaluated will be considered evaluable for non-target disease. The response assessment is based on the presence, absence, or unequivocal progression of the lesions.

Disease Parameters

Measurable disease. Measurable lesions are defined as those that can be accurately measured in at least one dimension (longest diameter to be recorded) as ≥ 6 mm by calipers on clinical examination. All tumor measurements must be recorded in millimeters (or decimal fractions of centimeters).

Non-measurable disease. All other lesions (or sites of disease), including small lesions (longest diameter < 6 mm) are considered non-measurable disease.

Note: Cystic lesions that meet the criteria for radiographically defined simple cysts should not be considered as malignant lesions (neither measurable nor non-measurable) since they are, by definition, simple cysts.

“Cystic lesions” thought to represent cystic metastases can be considered as measurable lesions if they meet the definition of measurability described above. However, if non-cystic lesions are present in the same patient, these are preferred for selection as target lesions.

Target lesions. All measurable lesions up to a maximum of 5 lesions in total, representative of all involved organs, should be identified as **target lesions** and recorded and measured at baseline. Target lesions should be selected on the basis of their size (lesions with the longest diameter), but in addition should be those that lend themselves to

reproducible repeated measurements. It may be the case that, on occasion, the largest lesion does not lend itself to reproducible measurement in which circumstance the next largest lesion that can be measured reproducibly should be selected. A sum of the diameters (longest for non-nodal lesions, short axis for nodal lesions) for all target lesions will be calculated and reported as the baseline sum diameters. The baseline sum diameters will be used as reference to further characterize any objective tumor regression in the measurable dimension of the disease. All target lesions will also be injected lesions.

Non-target lesions. All other lesions (or sites of disease) including any measurable lesions over and above the 5 target lesions should be identified as **non-target lesions** and should also be recorded at baseline. Measurements of these lesions are not required, but the presence, absence, or in rare cases unequivocal progression of each should be noted throughout follow-up. All non-target lesions will not be injected with T-VEC.

Methods for Evaluation of Measurable Disease

All measurements should be taken and recorded in metric notation using a ruler or calipers. All baseline evaluations should be performed as closely as possible to the beginning of treatment and never more than 4 weeks before the beginning of the treatment.

Clinical lesions. Clinical lesions will only be considered measurable when they are superficial (e.g., skin nodules and palpable lymph nodes) and ≥ 6 mm diameter as assessed using calipers. Documentation by color photography at baseline, including a ruler to estimate the size of the lesion, is recommended.

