7.2 PARTICIPANT DISCONTINUATION/WITHDRAWAL FROM THE STUDY

Participants are free to withdraw from participation in the study at any time upon request.

An investigator may discontinue or withdraw a participant from the study for the following reasons:

- Pregnancy
- Significant study intervention non-compliance
- If any clinical adverse event (AE), laboratory abnormality, or other medical condition or situation occurs such that continued participation in the study would not be in the best interest of the participant
- Disease progression which requires discontinuation of the study intervention
- If the participant meets an exclusion criterion (either newly developed or not previously recognized) that precludes further study participation
- Participant unable to receive T-VEC injection for ≥ 4 weeks (two consecutive doses).

The reason for participant discontinuation or withdrawal from the study will be recorded within the patient's medical record and OnCore and/or the Clinical Trial Management System (CTMS). Subjects who sign the informed consent form but do not receive the study intervention may be replaced. Subjects who sign the informed consent form, receive the study intervention, and subsequently withdraw, or are withdrawn or discontinued from the study prior to becoming evaluable for objective response, may be replaced.

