9.3 POPULATIONS FOR ANALYSES

The analysis datasets (e.g., which participants will be included in each analysis) include the following:

- Intention-to-Treat (ITT) Analysis Dataset
- Safety Analysis Dataset: defines the subset of participants for whom safety analyses will be conducted (e.g., participants who took at least one dose of study intervention)
- Per-Protocol Analysis Dataset: defines a subset of the participants in the full analysis (ITT) set who complied with the protocol sufficiently to ensure that these data would be likely to represent the effects of study intervention according to the underlying scientific model (e.g., participants who took at least 80% of study intervention for 80% of the days within the maintenance period)

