9.4.2 ANALYSIS OF THE PRIMARY EFFICACY ENDPOINT(S)

Our primary endpoint for this analysis will be confirmed overall response rate (ORR) in injected lesions based on modified RECIST criteria appropriate for cutaneous neoplasms (ORR = complete response + partial response)

According to the Simon's two-stage design, after testing the treatment on 8 patients in the first stage, the trial will be terminated if 1 or fewer responds. If the trial goes on to the second stage, a total of 13 patients will be studied. If the total number responding is less than or equal to 3, the treatment is rejected. Please see Sample Size description above for further details.

In addition, we will construct a 95% exact confidence interval for the ORR.

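### The denominator of the primary ORR, its exact 95% CI and the Simon counts is stated inconsistently and assigned to no analysis set, so early failures can be left out and replaced

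*Combined protocol and SAP*

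**What the plan says.** Several places read as a count of enrolled or treated patients. The synopsis and Section 4.1 accrue 8 patients, then enroll 5 more for a total of 13. The synopsis gives the study population as thirteen patients. The synopsis and Section 3 define the ORR as a proportion of patients, without restriction to evaluable ones. Section 9.4.2 says that "after testing the treatment on 8 patients in the first stage, the trial will be terminated if 1 or fewer responds".

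Two other places point to a count of evaluable patients. Section 8.1.2.1 limits evaluability for objective response to patients with measurable disease at baseline who "have received at least three injections at the 10^8 dose level, and have had their disease re-evaluated will be considered evaluable for response", and adds: "These patients will have their response classified according to the definitions stated below". Section 7.2 lists among the reasons for withdrawal "Disease progression which requires discontinuation of the study intervention", and says that treated patients who withdraw, or are "withdrawn or discontinued from the study prior to becoming evaluable for objective response, may be replaced". That sentence does not restrict the reason for leaving.

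Section 9 does not settle the matter. Section 9.3 lists an "Intention-to-Treat (ITT) Analysis Dataset" without saying who is in it, then defines the per-protocol set as "a subset of the participants in the full analysis (ITT) set". It assigns no set to the ORR, and the response-evaluable set of 8.1.2.1 is not on its list. Section 9.4.2 adds that "we will construct a 95% exact confidence interval for the ORR", again without a denominator. Sections 9.2 and 9.4.6 repeat the stage counts without a population.

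**The concern.** Whether a patient becomes evaluable depends partly on outcome. A patient who progresses and is withdrawn before the third 10^8 injection can be left unclassified and replaced by someone who may last longer. No section says that such a patient counts as a non-responder.

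The decisions turn on small counts: at least 2 responses in 8, and at least 4 in 13. Leaving out one or two early failures changes the estimate and its interval and can change who fills the stage counts. A reader of the result could not tell whether it describes everyone treated or only those who stayed about 8 weeks. The plan also does not say which of these groups P0 = 10% and P1 = 40% describe.

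**Working it through.** **1. When a patient becomes evaluable.** The Schedule of Activities and Section 6.1.2.1 put the first injection (10^6) at week 1, the second three weeks later, and the rest every two weeks. The 10^8 injections therefore fall at weeks 4, 6 and 8, and the third is at about week 8.

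**2. The plan's own figures.** Inputs from 9.2: n1 = 8, stop at 1 or fewer; n = 13, reject the treatment at 3 or fewer; P0 = 0.10, P1 = 0.40. With X1 ~ Bin(8, p) and X2 ~ Bin(5, p):

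- PET = P(X1 ≤ 1). At p = 0.10: 0.4305 + 0.3826 = 0.813.
- Expected N = 8 + 5(1 − PET) = 8 + 5 × 0.1869 = 8.93.
- P(declare active) = Σ over x1 ≥ 2 of P(X1 = x1) × P(X2 ≥ 4 − x1). At p = 0.10: 0.1488 × 0.0815 + 0.0331 × 0.4095 + 0.0050 = 0.0307. At p = 0.40: 0.8015.

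These match the stated 0.813, 8.93, 0.031 and 0.198 (1 − 0.8015). The design arithmetic is not in dispute.

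**3. Effect on the estimate.** Take 4 responders among 13 evaluable patients, with two early failures replaced along the way (an illustration). Clopper-Pearson 95% intervals:

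- 4/13 = 30.8% (9.1% to 61.4%)
- 4/15 = 26.7% (7.8% to 55.1%)

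This comparison does not depend on how P0 is read.

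**4. Range for early failures.** Let f be the share of treated patients who fail before becoming evaluable. The documents do not give f, so it is an assumption. Suppose no early failure responds, all leave the study and all are replaced. A true all-treated rate of 10% then appears among evaluable patients as q = 0.10/(1 − f). The expected number replaced is f/(1 − f) times the expected number of evaluable patients, which is 8 + 5(1 − PET at q).

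| f | q | PET at q | Expected evaluable | Expected replaced | Replaced if all 13 places are filled, 13f/(1 − f) |
|---|---|---|---|---|---|
| 5% | 10.5% | 0.797 | 9.01 | 0.5 | 0.7 |
| 10% | 11.1% | 0.779 | 9.10 | 1.0 | 1.4 |
| 20% | 12.5% | 0.736 | 9.32 | 2.3 | 3.25 |

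**5. Type I error (secondary and conditional).** If, in addition, P0 = 10% refers to all treated patients, the probability of declaring activity at q is 0.036, 0.043 or 0.062 at f = 5%, 10% or 20%. It equals 0.050 at f = 0.141. If P0 refers to evaluable patients, it stays at 0.031.

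**6. Power cost of an all-treated count.** If P1 = 40% was meant for evaluable patients, the all-treated rate is 0.40(1 − f) = 0.38, 0.36 or 0.32. The rejection probability is then 0.76, 0.71 or 0.61, against 0.80.

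**The case against.** The strongest reply is that the plan already implies the right count. Accruing 8 and enrolling 5 more to reach 13, testing treatment on 8 patients, and a proportion of patients all read naturally as enrolled or treated patients. This stands in part. A reader might infer that the plan is silent on the denominator, and that is not so: the defect is unreconciled wording. But the enrolled reading cannot simply be taken to prevail, because 8.1.2.1 withholds classification from the same patients whom 7.2 allows to be replaced, and nothing names the denominator of the CI.

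The second reply is that the route to bias is narrow. Withdrawal and replacement are both optional. Section 7.1 says that stopping T-VEC is not leaving the study. Section 6.1.2.3 lets some patients with new locoregional disease continue treatment, so some early progressors could reach three 10^8 injections. Some early losses will also have nothing to do with outcome. All of this stands, and it narrows the route without closing it: 7.1 also lists progression as a reason to stop treatment, and a patient who remains on study with fewer than three 10^8 injections is still unclassified under 8.1.2.1.

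The third reply is that an evaluable-only rule is coherent if P0 and P1 are stated for evaluable patients. That is correct, and the fix allows for it. Finally, the example shifts the estimate by about 4 points (30.8 − 26.7) inside an interval about 52 points wide (61.4 − 9.1). The shift is small next to the sampling error, but it is systematic and avoidable.

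**Conclusion.** The concern holds as a conflict between sections over the primary denominator, with no analysis set assigned to resolve it. If the evaluable-only and replacement rules are followed and the patients left out are non-responders, the ORR is biased upward as an estimate for treated patients. With two such patients the estimate is 30.8% rather than 26.7%.

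Two stronger readings are tempting and are not supported. One is that the plan requires early failures to be excluded; it only permits this. The other is that the true type I error exceeds its target. The stated 0.031 stands unless P0 refers to all treated patients, no early failure responds, and all of them leave and are replaced. Even then the 0.050 target holds until f reaches about 14%, and the documents give no value of f.

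This should be fixed, preferably before the stage 1 count. The sample size calculation itself is sound.

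**What to change.** Reconcile Sections 4.1, 7.2, 8.1.2.1, 9.3 and 9.4.2:

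- Define the primary ORR, its exact 95% CI and both Simon decisions on all patients who receive at least one T-VEC injection.
- Count a patient with a confirmed CR or PR (per 8.1.2.3 and 9.4.2, at the protocol's stated time point, which Section 3 gives as 24 weeks) as a responder, whatever the number of injections. Count every other treated patient as a non-responder.
- For the Simon counts, limit replacement to consented patients who are never treated.
- Keep the three-injection set as a labelled sensitivity analysis.
- State which population P0 = 10% and P1 = 40% describe.

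If the sponsor prefers an evaluable-only decision rule, state that P0 and P1 refer to evaluable patients, allow replacement only for reasons unrelated to outcome, and report the all-treated ORR with its exact 95% CI beside the evaluable one.

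The cost is wording, with no added procedures. The reported ORR may be lower. If P1 was meant for evaluable patients, power on the all-treated count falls to the values in step 6 of the working and should be restated; the evaluable-only alternative avoids that loss.

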8.1.2.2 GUIDELINES FOR EVALUATION OF CLINICAL DISEASE

All measurements of a palpable lesion should be taken and recorded in metric notation using a ruler or calipers at each study visit. If the lesion is not present, then it should be noted as such in the patient EMR.

The same method of assessment and the same technique should be used to characterize each identified and reported lesion at baseline and during follow-up.

8.1.2.3 RESPONSE CRITERIA

Evaluation of Target Lesions

Complete Response (CR): Disappearance of all target lesions.

Partial Response (PR): At least a 30% decrease in the sum of the diameters of target lesions, taking as reference the baseline sum diameters.

Progressive Disease (PD): At least a 20% increase in the sum of the diameters of target lesions, taking as reference the smallest sum on study (this includes the baseline sum if that is the smallest on study). (Note: the appearance of one or more new lesions is also considered progression).

Stable Disease (SD): Neither sufficient shrinkage to qualify for PR nor sufficient increase to qualify for PD, taking as reference the smallest sum diameters while on study.

Evaluation of Non-Target Lesions

Complete Response (CR): Disappearance of all non-target lesions and normalization of tumor marker level.

Progressive Disease (PD): Appearance of one or more new lesions and/or unequivocal progression of existing non-target lesions. Unequivocal progression should not normally trump target lesion status. It must be representative of overall disease status change, not a single lesion increase.

Although a clear progression of “non-target” lesions only is exceptional, the opinion of the treating physician should prevail in such circumstances, and the progression status should be confirmed at a later time by the review panel (or Principal Investigator). Photography of these changes is recommended.

Evaluation of Best Overall Response

The best overall response is the best response recorded from the start of the treatment until disease progression/recurrence (taking as reference for progressive disease the smallest measurements recorded since the treatment started). The patient's best response assignment will depend on the achievement of both measurement and confirmation criteria.

Overall Response Criteria

Target Lesions	Non-Target Lesions	New Lesions	Overall Response	Best Overall Response when Confirmation is Required
CR	CR	No	CR	≥ 4 wk Confirmation
CR	Non-CR/Non-PD	No	PR	≥ 4 wk Confirmation
CR	Not evaluated	No	PR	
PR	Non-CR/Non-PD/not evaluated	No	PR	
SD	Non-CR/Non-PD/not evaluated	No	SD	Documented at least once ≥ 4 wk from baseline
PD	Any	Yes or No	PD	No prior SD, PR, or CR
Any	PD***	Yes or No	PD	
Any	Any	Yes	PD	

*** In exceptional circumstances, unequivocal progression in non-target lesions may be accepted as disease progression.

Note: Patients with a global deterioration of health status requiring discontinuation of treatment without objective evidence of disease progression at that time should be reported as “symptomatic deterioration.” Every effort should be made to document the objective progression even after discontinuation of treatment.

Objective response—Response and progression will be evaluated in this study using a primary endpoint of objective response, which is defined as either complete or partial response

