5 STUDY POPULATION

5.1 INCLUSION CRITERIA

To be eligible to participate in this study, an individual must meet all of the following criteria:

1. Provision of signed and dated informed consent form
2. Stated willingness to comply with all study procedures and availability for the duration of the study
3. Adult male or female, aged 18 years and over
4. Patients must have histologically confirmed CA without visceral or CNS metastases, with resection deemed of no benefit by technical or oncologic principles, and have progressed on at least one line of systemic therapy
5. Patients must have measurable disease, defined as at least one lesion that can be accurately measured in at least one dimension (longest diameter to be recorded by digital photography) as ≥ 6 mm with calipers or a ruler.
6. Eastern Cooperative Oncology Group performance status 0-1 (Karnofsky $\geq 70\%$).
7. Patients must have normal organ and marrow function as defined below:
 - a. Hematological
 - i. - Absolute neutrophil count $\geq 1500/\text{mm}^3$ ($1.5 \times 10^9/\text{L}$)
 - ii. - Platelet count $\geq 75,000/\text{mm}^3$ ($7.5 \times 10^9/\text{L}$)
 - iii. - Hemoglobin $\geq 8 \text{ g/dL}$ (without need for hematopoietic growth factor or transfusion support)
 - b. Renal
 - i. - Serum creatinine $\leq 1.5 \times$ upper limit of normal (ULN), OR 24-hour creatinine clearance $\geq 60 \text{ mL/min}$ for subject with creatinine levels $> 1.5 \times$ ULN. (Note: Creatinine clearance need not be determined if the baseline serum creatinine is $\leq 1.5 \times$ ULN. . Creatinine clearance should be determined per institutional standard).
 - c. Hepatic
 - i. - Serum bilirubin $\leq 1.5 \times$ ULN OR direct bilirubin \leq ULN for a subject with total bilirubin level $> 1.5 \times$ ULN
 - ii. - Aspartate aminotransferase (AST) $\leq 2.5 \times$ ULN OR $< 5 \times$ ULN, if liver metastases present and injection does not involve a visceral lesion
 - iii. - Alanine aminotransferase (ALT) $\leq 2.5 \times$ ULN OR $< 5 \times$ ULN, if liver metastases present and injection does not involve a visceral lesion
 - d. Coagulation
 - i. - International normalization ratio (INR) or prothrombin time (PT) $\leq 1.5 \times$ ULN, unless the subject is receiving anticoagulant therapy, in which case PT and partial thromboplastin time (PTT)/ activated PTT (aPTT) must be within therapeutic range of intended use of anticoagulants.

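### Target-lesion progression has no minimum increase in millimetres, so in patients with small target sums a 1 to 2 mm reading difference can end a response

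*Combined protocol and SAP*

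**What the plan says.** Section 8.1.2.3 sets two thresholds on the same sum. Partial response is "At least a 30% decrease in the sum of the diameters of target lesions, taking as reference the baseline sum diameters". Progression is "At least a 20% increase in the sum of the diameters of target lesions, taking as reference the smallest sum on study", or a new lesion. No section adds a minimum rise in millimetres. No section asks for a second reading before target-lesion progression is declared; only progression confined to non-target lesions is to be confirmed later.

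The sums can be small. Section 5.1, item 5, asks for "at least one lesion that can be accurately measured in at least one dimension", and both 5.1 and 8.1.2.1 set the limit at 6 mm. Target lesions are "All measurable lesions up to a maximum of 5 lesions in total". Diameters are recorded in millimetres or decimal centimetres. Under 8.1.2, "patients will be re-evaluated for response every 2 weeks prior to injection", with calipers and/or a ruler.

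The first progression has four consequences. It closes best overall response (8.1.2.3), ends response duration (8.1.2.4), is a PFS event (8.1.2.5) and is a reason to stop treatment (7.1, item 2). The primary analysis in 9.4.2 uses confirmed response; the table in 8.1.2.3 shows confirmation at 4 weeks or more.

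**The concern.** A percentage threshold on a small sum becomes a threshold of one or two millimetres, which is the size of a reading difference. The reference is the smallest sum so far, so each chance low reading lowers the bar for all later visits, and readings are frequent. A patient who is responding, or simply stable, can be classed as progressed without growth.

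If this happens before confirmation, a true response is missing from the primary endpoint. If it happens later, response duration and PFS are cut short. With 13 patients, and four responses needed to reject the null hypothesis, a few misclassified patients matter.

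**Working it through.** **1. The plan's own figures.** The design stops with 1 or fewer responses in 8 and rejects the treatment with 3 or fewer in 13. At P0 = 0.10 the probability of early termination is 0.9^8 + 8 × 0.1 × 0.9^7 = 0.813, and the expected sample size is 8 + (1 − 0.813) × 5 = 8.93. The exact two-stage calculation gives a type I error of 0.0307 and, at P1 = 0.40, a type II error of 0.1985. All agree with 9.2 and are not in question.

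**2. Smallest rise that counts as progression.** With smallest sum S in whole millimetres, the rise needed is the smallest whole k with k ≥ 0.20 × S.

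- S up to 5 mm: 1 mm. S up to 10 mm: 2 mm. S up to 25 mm: 5 mm or less.
- Readings 6, 4, 5 mm: 4/6 is −33%, a partial response; 5/4 is +25%, progression; 5/6 is still 17% below baseline.
- Readings 8, 5, 6 mm: −37.5%, then +20%, so progression at 25% below baseline.
- Readings 6, 5, 6 mm: 6/5 = 1.20, progression at the baseline size.
- Five 6 mm lesions: 30 mm falls to 21 mm at partial response; progression then needs 0.20 × 21 = 4.2 mm, or 5 mm in whole units.

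This step needs no assumption beyond whole-millimetre reading.

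**3. Confirmed responses lost.** Simulation, 100,000 runs per case. Assumptions not in the documents: one lesion that shrinks steadily to half by week 16 and then stays there, independent normal reading error, whole-millimetre recording, 13 readings after baseline (weeks 2, 3, 4, then every 2 weeks to 24), confirmation at least 4 weeks later. Share of confirmed responses lost because progression was called first:

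| Error SD | 6 mm | 10 mm | 15 mm | 20 mm |
|---|---|---|---|---|
| 0.25 mm | 31% | 0% | 0% | 0% |
| 0.5 mm | 73% | 8% | <1% | 0% |
| 1 mm | 94% | 59% | 23% | 5% |

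A 5 mm minimum recovers nearly all of these.

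**4. False progression with no true change.** Same readings, one stable lesion of 6 / 10 / 15 / 20 mm: 26 / 4 / 0 / 0% at SD 0.25 mm; 89 / 68 / 2 / 0% at SD 0.5 mm; over 98 / over 98 / 76 / about 31% at SD 1 mm. With a 5 mm minimum, every one of these is 6% or less.

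For response duration and PFS, the sum after shrinkage is what counts. A lesion steady at 4 mm is falsely called progressed within the next two readings in 9%, 47% and 67% of runs at the three SDs; with a 5 mm minimum, in 0.2% or less. A lesion steady at 10 mm, for example one that began at 20 mm and halved, is falsely called within ten readings in 2.5%, 55% and 96%; with the minimum, in 0%, 0% and 3.5%.

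**5. Where the minimum helps little.** Stable lesions at SD 1 mm, 5 mm minimum in force: two 6 mm lesions about 47%, two 10 mm lesions about 47%, three 10 mm lesions about 49%.

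**6. Effect on power.** If a fraction f of true responses is lost, the effective rate is 0.40 × (1 − f). For f = 5%, 10% and 20% (an assumed range) it is 0.38, 0.36 and 0.32, and power falls from 0.80 to 0.76, 0.71 and 0.61.

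**The case against.** The strongest reply is that few patients may be exposed. Every measurable lesion up to five is a target, so a 6 mm sum requires a patient whose only measurable lesion is 6 mm. The population is locally advanced, not helped by resection and often multifocal, and the injection table in 6.1.2.2 runs to lesions above 5 cm. This stands as a limit on scope: no size distribution is given, so prevalence is unknown. The same table has bands for 0.5 to 1.5 cm and for 0.5 cm or less, so small lesions are foreseen.

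The inputs are also assumptions. Decimal centimetres do not fix the precision; without rounding, the stable 10 mm figure at SD 0.5 mm falls from 68% to 24% (the 6 mm figure stays near 88%). Section 8.1.1 lists no tumour measurement at weeks 2 and 3, although Table 1 does; with 11 readings the 10 mm figure is 60%. Selecting lesions for reproducibility (8.1.2.1) and keeping one technique (8.1.2.2) should reduce error. All of this is fair and is why a range is shown. Photographs (6.3, 6.4) document response and set no margin for progression.

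Two stronger readings are tempting. A reader might infer that a one-unit difference can end any response; that holds only for a smallest sum of 5 mm or less. A reader might also take the stable-lesion rates as lost ORR. They are not: at 10 mm and SD 0.5 mm, 68% of stable lesions are falsely called, but only about 8% of confirmed responses are lost.

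**Conclusion.** The gap is real and follows from the plan's own thresholds: for small target sums, 1 or 2 mm is progression. How much it matters depends on lesion sizes and reading error, neither of which the documents give. Under the stated assumptions the loss of confirmed responses is large for a single 6 mm lesion, modest at 10 mm with SD 0.5 mm, and negligible for baseline sums of about 15 to 20 mm or more unless error is near 1 mm. Response duration and PFS are more exposed, because shrinkage moves responders into the sensitive range.

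The documents do not support a claim that the trial's ORR is generally unreliable, or that false positives increase. The bias in ORR runs toward missing a true effect, and the stated type I error is not inflated. This is a worthwhile, inexpensive correction rather than a flaw in the design.

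**What to change.** For the analysis of ORR, response duration and PFS:

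- Define target-lesion progression as an increase of at least 20% and at least 5 mm in the sum over the smallest sum.
- State that reappearance after CR counts as recurrence, since 20% of a sum of 0 mm is undefined.
- Report the rule as now written as a sensitivity analysis.

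The 5 mm figure is a choice, not derived from the documents. For a lesion steady at 4 mm over two readings, a 2, 3 or 5 mm minimum leaves 7%, 0.1% and 0% false progression at SD 0.5 mm, and 33%, 10% and 0.2% at SD 1 mm.

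The cost is one clause and one extra analysis, with the visit schedule unchanged. The downside is that true growth of very small lesions is called later, and not by a trivial amount: from 4 mm, progression needs 9 mm (+125%, and 50% above a 6 mm baseline); from 6 mm it needs 11 mm (+83%). The clause also gives limited protection to multi-lesion sums if error is near 1 mm.

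Section 7.1 stops treatment on progression as defined in 8.1.2.3, whereas 6.1.2.3 uses a two-fold increase within 4 months. The sponsor must reconcile these passages separately, and the new clause should be labelled as an analysis definition so that it does not change either by default. No stopping rule is proposed here. Readings also need to continue after a 20% rise for the new definition to be assessed; 7.1 already asks that remaining study procedures be completed after T-VEC is discontinued.
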